1. PROTOCOL SUMMARY

1.1. Synopsis

Short Title: A Phase 1 Study of Single and Multiple Ascending Doses of PF-07059013 in Healthy Adults

Rationale

PF-07059013 is a novel small molecule allosteric modulator of hemoglobin that is currently being developed for the treatment of Sickle Cell Disease. The purpose of the study is to evaluate the safety, tolerability, pharmacokinetics (PK) and pharmacodynamic (PD) of single and multiple ascending oral doses of PF-07059013 in healthy adult participants.

Additionally, effects of different formulations and food on parameters, including PK may be explored. This study is the first time that PF-07059013 will be administered to humans, and the results obtained from this study will inform future clinical development of PF-07059013. Based on modulation of the PD parameters (p20 and p50), results from Part 2 of this study may provide a demonstration of pharmacology for modulation of hemoglobin oxygen affinity.

Objectives and Endpoints

Objectives	Endpoints
Primary: 
• Part 1 and 2• To evaluate safety and tolerability of single and multiple escalating oral doses of PF-07059013 suspension administered in healthy adult participants.	Primary: 
• Assessment of AEs, clinical laboratory tests, vital signs (including blood pressure, pulse rate, respiratory rate and oral temperature) and cardiac conduction intervals and heart rate as assessed via 12-lead electrocardiogram (ECG).
Secondary: 
• Part 1 and 2• To characterize the blood and plasma exposures of PF-07059013 following administration of single and multiple oral suspension doses in healthy adult participants.	Secondary: 
• PF-07059013 blood and plasma exposure parameters, as data permit:
• Part 1• C_{max}, T_{max}, and AUC_{last}.• Part 2• C_{max}, T_{max}, AUC_{τ}, on Days 1, 7 and 14.

• Part 1 and 2• To evaluate the PD profile of PF-07059013 following administration of single and multiple oral doses of suspension in healthy adult participants.	
• p20 and p50 change from baseline.

Overall Design

This study consists of 3 parts, with ongoing review of safety, tolerability, PK and PD data planned. Part 1 comprises of 4 periods with 2 interleaving cohorts of healthy adult participants. Part 1 Period 1 to 3 is investigator- and participant-blinded, sponsor-open, randomized, single ascending dose, with 3-period placebo substitution crossover, and Period 4 will be open-label.

Part 2 of this study will be investigator- and participant-blinded, sponsor-open, randomized, placebo-controlled, sequential, multiple ascending dose, with 3 planned cohorts of healthy adult participants. Two additional cohorts of healthy adult participants may be included to permit assessment of any of the following: repeat of a previously administered dose level; studying additional dose levels as dictated by the evaluated safety, tolerability or PK of earlier dose levels; or any other assessment needed to meet the objectives of this study.

Part 3 of this study will be an open-label, randomized, 4-period crossover, single dose assessment of formulation and/or food effects in healthy adult participants.

Number of Participants

A total of approximately 50 (2 planned cohorts with approximately 9 in each cohort for Part 1 and 4 planned cohorts with approximately 8 in each cohort for Part 2 and 3) or up to approximately 70 (including optional Cohorts 6 and 7 and possible expansion to Part 3) healthy adult participants will be randomized.

Intervention Groups and Duration

For all parts of the study, participants will be screened within 28 days of their first dose of investigational product. Participants will be admitted to the CRU on Day -1 and may be discharged at investigator discretion following completion of assessments per [SoA](#).

Part 1 – Single Ascending Dose

Each participant may receive up to 3 single oral doses of PF-07059013 suspension and up to 1 placebo dose. For Period 1 to 3, at each period, approximately 6 participants will receive a single dose of PF-07059013 suspension formulated with polymer, and approximately 3 participants will receive placebo. In Period 4, a single dose of PF-07059013 suspension, formulated without polymer, will be administered at a dose level that has been previously administered in the same cohort. Between each dose administration to a given participant there will be a washout interval of at least 14 days. The washout interval may be adjusted based on data emerging from previous cohorts/periods. An on-site visit is scheduled for Day 8 (± 1 day) of Period 3 and 4, and telephone follow-up contact will occur 28 to 35 days after the last dose of investigational product in the final period. The total planned duration of participation, from the Screening visit to the Follow-up phone call, is approximately 15 weeks.

Part 2 – Multiple Ascending Dose

Each participant may receive multiple oral doses of PF-07059013 suspension (either with or without polymer, depending on results from Part 1) or placebo, over a duration of 14 days, depending on randomization. Participants will be required to stay at the CRU for the duration of the treatment phase. An on-site follow-up visit and a telephone follow-up contact will take place at Day 21 (± 1 day) and between Day 42-49, respectively. The total planned duration of participation, from the Screening visit to the Follow-up phone call, is approximately 10 weeks.

Part 3 – Formulation and Food Effects

Each participant may receive single oral dose of suspension with different formulations, or tablet, either under fasted condition or following a high-fat/high-caloric meal. Between each dose administration to a given participant there will be a washout interval of at least 14 days. The washout interval may be adjusted based on data emerging from previous cohorts/periods. A telephone follow-up contact will occur 28 to 35 days after the last dose of investigational product in the final period. The total planned duration of participation, from the Screening visit to the Follow-up phone call, is approximately 15 weeks.

Data Monitoring Committee or Other Independent Oversight Committee: No

[figure not shown]
[figure not shown]
[figure not shown]
Statistical Methods

Detailed methodology for summary and statistical analyses of the data collected in this study is outlined here and further detailed in a statistical analysis plan (SAP), which will be maintained by the sponsor.

No formal sample size calculation or statistical hypothesis testing will be performed in this study. Cohort size has been chosen to ensure appropriate sample size to provide adequate safety, toleration and PK information at each dose level and to provide a placebo comparison group, while minimizing exposure to humans of a new biologic entity. Safety data will be presented in tabular and/or graphical format and summarized descriptively, where appropriate. PK and PD data will be listed and descriptively summarized as required.

1.2. Schema

Sample study design schematics of Study Part 1, 2 and 3 are provided below. Doses are provided for illustrative purpose only.

Sample Dosing Scheme (Part 3 – Formulation and Food Effect)

Cohort		Period 1	Period 2	Period 3	Period 4
8	N=2	A	B	C	D
	N=2	D	A	B	C
	N=2	C	D	A	B
	N=2	B	C	D	A

Treatment A: PF-07059013 oral suspension (Small particle size), fasted.

Treatment B: PF-07059013 oral suspension (Small particle size), fed.

Treatment C: PF-07059013 oral suspension (Moderate particle size), fasted.

Treatment D: PF-07059013 oral tablet, fasted.

1.3. Schedule of Activities

The SoA table provides an overview of the protocol visits and procedures. Refer to the **STUDY ASSESSMENTS AND PROCEDURES** section of the protocol for detailed information on each procedure and assessment required for compliance with the protocol.

The investigator may schedule visits (unplanned visits) in addition to those listed in the SoA table, in order to conduct evaluations or assessments required to protect the well-being of the participant.

A. Part 1 SoA – Single Ascending Dose

Visit Identifier ^a	Screening	Period 1 to Period 4 ^b												F/U Contact ^c	E/T		
		Day -28 to Day -2	Day -1	Day 1						Day 2		Day 3	Day 4	Day 5	Visit ^d Day 8±1		
Hours Post dose				0 ^e	0.5	1	2	5	8	12	24	36	48	72	96	168	
Informed consent	X																
CRU confinement		X	→	→	→	→	→	→	→	→	→	→	→	→	X		
Inclusion/exclusion criteria	X	X ^o															
Medical/medication history	X																
Demography	X																
Physical exam (height and weight at Screening, only) ^f	X	X														X	
12-Lead ECG ^g	X		X	X	X	X	X	X	X	X	X	X	X	X	X	X	
Supine blood pressure ^h and pulse rate	X		X	X	X	X	X	X	X	X	X	X	X	X	X	X	
Orthostatic blood pressure, respiratory rate and oral temperature			X			X		X		X							
Continuous cardiac telemetry monitoring		X ⁱ	X	→	→	→	→	→	→	X							
Contraception check	X	X												X	X	X	
Serious and nonserious adverse event monitoring	X	→	→	→	→	→	→	→	→	→	→	→	→	→	X	X	
Study intervention administration ^j			X														

A. Part 1 SoA – Single Ascending Dose

Visit Identifier ^a	Screening	Period 1 to Period 4 ^b												F/U Contact ^c	E/T	
		Day -28 to Day -2	Day -1	Day 1						Day 2		Day 3	Day 4	Day 5	Visit ^d Day 8±1	
Hours Post dose		0 ^e	0.5	1	2	5	8	12	24	36	48	72	96	168		
Blood sampling:																
HIV, HBsAg, HBsAb, HBcAb, HCVAb, PT/INR, aPTT and serum FSH (postmenopausal females only)	X															
Safety laboratory ^k	X	X						X		X				X	X	
Lactate ^l	X	X						X		X				X	X	
Ferritin and C reactive protein	X	X												X	X	
Pharmacokinetic			X	X	X	X	X	X	X	X	X	X ⁿ	X ⁿ	X	X	
p20 and p50			X					X							X	
CCI				X												
Urine sampling:																
Urine drug and cotinine testing	X	X														
Urinalysis (and microscopy, if needed)	X	X								X				X	X	

Abbreviations: → = ongoing/continuous event; aPTT = activated partial thromboplastin time; E/T = early termination; F/U = follow-up; HBcAb = hepatitis B core antibody; HBcAg = hepatitis B core antigen; HBsAg = hepatitis B surface antigen; HCVAb = hepatitis C antibody; HIV = human immunodeficiency virus; CRU = clinical research unit; ECG = electrocardiogram; FSH = follicle-stimulating hormone; H= hour; p20 = oxygen pressure at which 20% of the hemoglobin in a given blood sample is oxygenated; p50 = oxygen pressure at which 50% of the hemoglobin in a given blood sample is oxygenated; PT/INR = prothrombin time/internationalized normalized ratio.

A. Part 1 SoA – Single Ascending Dose

Visit Identifier ^a	Screening	Period 1 to Period 4 ^b											F/U Contact ^c	E/T	
Days Relative to Day 1	Day -28 to Day -2	Day -1	Day 1					Day 2		Day 3	Day 4	Day 5	Visit ^d Day 8±1	28-35 Days	
Hours Post dose			0 ^e	0.5	1	2	5	8	12	24	36	48	72	96	168

- a. **Visit Identifier:** Day relative to start of study treatment (Day 1).
- b. **Period 1 to Period 4:** Washout duration of at least 14 days between periods. May be adjusted based on emerging data.
- c. **F/U Contact:** Follow-up phone call may occur via telephone and must occur 28 to 35 days after the last dose of investigational product in the final period.
- d. **Visit Day 8:** Only applicable for Period 3 and 4.
- e. **Day 1 0 H:** Predose sample collection/procedure, except for study treatment administration.
- f. **Physical Examination:** Complete physical examination will be conducted at Screening or upon admission (Day -1) in Period 1. Brief physical examination may be performed at other times, as appropriate, for findings during previous examination or new/open AEs, at investigator's discretion.
- g. **12-lead ECG:** Single at Screening, and triplicate at all other timepoints.
- h. **Supine blood pressure:** Where orthostatic blood pressure assessment will be conducted, supine blood pressure does not need to be repeated separately.
- i. **Continuous cardiac telemetry monitoring:** Baseline telemetry to be recorded for at least 2 hours between admission and prior to dosing in Period 1 only while awake. Post dose telemetry will continue for 12 hours after dosing for each period.
- j. **Study Treatment Administration:** Participants should fast for at least 10 hours prior to dosing. Refer to [Section 6.1.1](#) and [Section 5.3.1](#).
- k. **Safety laboratory:** Participants should fast for at least 4 hours prior to sample collection, except Day 1 eight hours postdose sample. Only chemistry panel is required for Day 1 eight hours postdose.
- l. **Lactate:** Unless needed for screening, review of data is not required prior to dosing but data up to at least 8 hours post dose will be reviewed prior to dose escalation.

CCI

- n. **Pharmacokinetic samples at 72 and 96 hours:** Only applicable for Period 2 to 4.
- o. **Inclusion/exclusion criteria Day -1:** Period 1 only.

B. Part 2 SoA – Multiple Ascending Dose

Visit Identifier ^a	Screening	Treatment Phase (all activities at 0H (predose) unless otherwise specified)																		Follow-up ^b		E/T			
		-28 to -2	-1	1 ^j	2	3	4	5	6	7 ^j	8	9	10	11	12	13	14 ^j	15	16	17	18	Visit: 21±1	Contact: 42-49		
Days Relative to Day 1																									
Informed consent	X																								
CRU confinement		X	→	→	→	→	→	→	→	→	→	→	→	→	→	→	→	→	→	→	X				
Inclusion/exclusion criteria	X	X																							
Medical/medication history	X																								
Demography	X																								
Physical exam (height and weight at Screening, only) ^c	X	X																					X		
12-Lead ECG ^d	X		X	X		X ^k			X			X ^k					X	X			X	X		X	
Supine blood pressure and pulse rate ^e	X		X	X		X ^k			X			X ^k					X	X			X	X		X	
Orthostatic blood pressure, respiratory rate and oral temperature			X							X								X			X				
Contraception check	X	X																			X	X	X	X	
Serious and nonserious adverse event monitoring	X	→	→	→	→	→	→	→	→	→	→	→	→	→	→	→	→	→	→	→	→	X	X		
Study intervention administration ^f			X	X	X	X	X	X	X	X	X	X	X	X	X	X	X	X	X						
Blood Sampling:																									
HIV, HBsAg, HBsAb, HBcAb, HCVAb, PT/INR, aPTT and serum FSH (postmenopausal females only)	X																								
Safety laboratory ^g	X	X	X	X		X			X			X					X			X	X		X		
Lactate ^h	X	X	X	X		X			X			X					X			X	X		X		
EPO ^h			X						X								X			X	X		X		
Reticulocytes ^h	X	X							X								X			X	X		X		
Ferritin & C reactive protein	X	X															X			X	X		X		
Pharmacokinetic ⁱ			X	X		X ^k			X	X		X ^k					X	X	X	X	X	X		X	
CCI																									
p20 and p50			X	X					X								X	X			X			X	
C																									
Urine Sampling:																									
Urine drug and cotinine testing	X	X																							
Urinalysis (and microscopy, if needed)	X	X			X	X			X			X					X			X	X		X		

B. Part 2 SoA – Multiple Ascending Dose

Visit Identifier ^a	Screening	Treatment Phase (all activities at 0H (predose) unless otherwise specified)																		Follow-up ^b		E/T		
		Days Relative to Day 1	-28 to -2	-1	1 ^j	2	3	4	5	6	7 ^j	8	9	10	11	12	13	14 ^j	15	16	17	18	Visit: 21±1	Contact: 42-49
CCI [REDACTED]																								

- a. **Visit Identifier:** Day relative to start of study treatment (Day 1).
- b. **Follow-up:** Onsite follow-up visit to occur between Day 20 to Day 22. Follow-up contact may occur via telephone and must occur 28 to 35 days from administration of the final dose of investigational product (ie, Day 42 to Day 49).
- c. **Physical Examination:** Complete physical examination will be conducted at Screening or upon admission (Day -1). Brief physical examination may be performed at other times, as appropriate, for findings during previous examination or new/open AEs, at investigator's discretion.
- d. **12-lead ECG:** Single at Screening, and triplicate at all other timepoints.
- e. **Supine blood pressure:** Where orthostatic blood pressure assessment will be conducted, supine blood pressure does not need to be repeated separately.
- f. **Study Treatment Administration:** Refer to [Section 6.1.1](#) and [Section 5.3.1](#).
- g. **Safety laboratory:** Participants should fast for at least 4 hours prior to sample collection, except 8 hours postdose sample. Only chemistry panel is required for 8 hours postdose.
- h. **Lactate, EPO, Reticulocytes:** Unless needed for screening, review of data is not required prior to dosing but lactate and EPO data up to at least Day 7, and reticulocyte data up to at least Day 14 will be reviewed prior to dose escalation. Refer to [Section 6.6.1](#) for details.
- i. **Pharmacokinetics:**
For dosing days - Samples will be collected predose, *where applicable*. For Day 1, 7 and 14, refer to [C List of Procedures for Part 2 Study Day 1, 7 and 14](#).
For post last dose - Day 15 samples will be collected 24H and 36H post last dose, Day 16 to 18 samples will be collected 48H, 72H and 96H post last dose respectively.
j. **Day 1, 7 and 14:** Refer to [C List of Procedures for Part 2 Study Day 1, 7 and 14](#) for details.
k. **Day 4 and 10:** PK samples, 12-lead ECG, supine blood pressure and pulse rate will be taken at predose and 8 hours postdose.
[REDACTED]

C. List of Procedures for Part 2 Study Day 1, 7 and 14

Hours Post dose	0 ^a	0.5	1	2	4	6	8	12	24
Continued CRU confinement	→	→	→	→	→	→	→	→	→
12-Lead ECG ^b	X	X	X	X	X	X	X	X	
Supine blood pressure ^c and pulse rate	X	X	X	X	X	X	X	X	
Orthostatic blood pressure, respiratory rate and oral temperature	X				X		X		
Serious and nonserious adverse event monitoring	→	→	→	→	→	→	→	→	→
Study intervention administration ^d	X								
Safety laboratory ^e	X ^g						X		
Lactate ^f	X ^g						X		
EPO (Day 7 and 14 only) ^f	X								
Reticulocytes (Day 7 and 14 only) ^f	X								
Ferritin & C reactive protein (Day 14 only)	X								
Pharmacokinetic	X	X	X	X	X	X	X	X	
CCI [REDACTED]	[REDACTED]	[REDACTED]	[REDACTED]	[REDACTED]	[REDACTED]	[REDACTED]	[REDACTED]	[REDACTED]	
p20 and p50	X						X		
Urinalysis (and microscopy, if needed)	X ^g								
Urine blank (Day 1 only)	X								
CCI [REDACTED]	[REDACTED]	[REDACTED]	[REDACTED]	[REDACTED]	[REDACTED]	[REDACTED]	[REDACTED]	[REDACTED]	

a. **0 H:** Predose sample collection.

b. **12-lead ECG:** Triplicate supine measurements.

c. **Supine blood pressure:** Where orthostatic blood pressure assessment will be conducted, supine blood pressure does not need to be repeated separately.

d. **Study Treatment Administration:** Refer to [Section 5.3.1](#) and [Section 6.1.1](#).

e. **Safety laboratory:** Participants should fast for at least 4 hours prior to sample collection, except 8 hours postdose samples. Only chemistry panel is required for 8 hours postdose samples.

f. **Lactate, EPO, Reticulocytes:** Unless needed for screening, review of data is not required prior to dosing but lactate and EPO data up to at least Day 7, and reticulocyte data up to at least Day 14 will be reviewed prior to dose escalation, and cumulative results will be reviewed as they become available. Refer to [Section 6.6.1](#).

g. **Safety laboratory and lactate 0 H:** For Day 7 and 14 only.

D. Part 3 SoA

Visit Identifier ^a	Screening	Period 1 to Period 4 ^b											F/U Contact ^c	E/T	
Days Relative to Day 1	Day -28 to Day -2	Day -1	Day 1						Day 2		Day 3	Day 4	Day 5	28-35 Days	
Hours After Dose			0 ^d	0.5	1	2	5	8	12	24	36	48	72	96	
Informed consent	X														
CRU confinement		X	→	→	→	→	→	→	→	→	→	→	→	X	
Inclusion/exclusion criteria	X	X ^k													
Medical/medication history	X														
Demography	X														
Physical exam (height and weight at Screening, only) ^e	X	X												X	
12-Lead ECG ^f	X		X			X	X	X	X		X		X	X	
Supine blood pressure and pulse rate	X		X		X	X	X	X	X		X		X	X	
Respiratory rate and oral temperature			X							X			X		
Contraception check	X	X											X	X	
Serious and nonserious adverse event monitoring	X	→	→	→	→	→	→	→	→	→	→	→	→	X	
High-fat/High-caloric meal			X ^g												
Study intervention administration			X ^g												
Blood sampling:															
HIV, HBsAg, HBsAb, HBcAb, HCVAb, PT/INR, aPTT and serum FSH (postmenopausal females only)	X														
Safety laboratory ^h	X	X								X			X	X	
Lactate ⁱ	X	X								X			X	X	
Ferritin and C reactive protein	X	X											X	X	
Pharmacokinetic			X	X	X	X	X	X	X	X	X	X	X	X	
CCI [REDACTED]															
Urine sampling:															
Urine drug testing	X	X													
Urinalysis (and microscopy, if needed)	X	X								X			X	X	

D. Part 3 SoA

Visit Identifier ^a	Screening	Period 1 to Period 4 ^b											F/U Contact ^c	E/T
		Days Relative to Day 1	Day -28 to Day -2	Day -1		Day 1				Day 2		Day 3	Day 4	Day 5
				Hours After Dose	0 ^d	0.5	1	2	5	8	12	24	36	48

- a. **Visit Identifier:** Day relative to start of study treatment (Day 1).
- b. **Period 1 to Period 4:** Washout duration of at least 14 days between periods. May be adjusted based on emerging data.
- c. **F/U Contact:** Follow-up contact may occur via telephone and must occur 28 to 35 days after the last dose of investigational product in the final period.
- d. **Day 1 0 H:** Predose sample collection/procedure, except for study treatment administration.
- e. **Physical Examination:** Complete physical examination will be conducted at Screening or upon admission (Day -1) in Period 1. Brief physical examination may be performed at other times, as appropriate, for findings during previous examination or new/open AEs, at investigator's discretion.
- f. **12-lead ECG:** Single at Screening, and triplicate at all other timepoints.
- g. **Study Treatment Administration & Meal:** As determined by randomization scheme, dosing to occur with either high-fat/high-caloric meal (ie, provided approximately 30 mins prior to dosing at 0H and expected to be completed approximately 10 minutes prior to dosing) **or** following an overnight fast of at least 10-hours, without breakfast. Refer to [Section 5.3.1](#) and [Section 6.1.1](#).
- h. **Safety laboratory:** Participants should fast for at least 4 hours prior to sample collection.
- i. **Lactate:** Unless needed for screening, review of data is not required prior to dosing; accumulative results will be reviewed as they become available.
- C**
C
C
- k. **Inclusion/exclusion criteria Day -1:** Period 1 only.

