To better understand and guide formulation development for future clinical studies, preliminary assessment of a tablet formulation and examination of different particle size is also planned.

Since the dose in this Part (refer to [Section 4.3.3.3](#)) will be selected based on observed safety and tolerability of single doses in Part 1 and the dose selected will be lower than the highest dose tested in Part 1, standard safety monitoring will be used in this part of the study, without placebo control, and without on-site visit following discharge.

For all parts of the study

Considering the nonclinical safety studies with PF-07059013 in mice and dogs (see [Section 2.2.3](#)), the standard safety assessments used by the sponsor in trials administering investigational product for the first time to humans are deemed suitable (see [Appendix 2: Clinical Laboratory Tests](#)). In addition to the standard safety assessments, levels of lactate (Part 1 to 3), EPO and reticulocyte count (Part 2 only) will also be monitored to evaluate the potential risk of reduction in tissue oxygen delivery per unit volume of blood, for this class of mechanism. Due to the long half-life of RBC and lag for EPO stimulation, any potential effects on reticulocyte count and EPO will likely only manifest after a sustained period, hence assessments are planned for Part 2, from Day 7 onwards for EPO and reticulocyte count. Ferritin levels and respiratory rate will be also assessed based on non-adverse findings in the nonclinical studies with PF-07059013 (see [Section 2.2.3](#)), with ferritin assessment planned on/after Day 5 due to physiologic rationale that this is likely the earliest point at which modulation of ferritin could be detected.

To ensure that participants with undiagnosed hematological conditions and elevated baseline lactate are not enrolled, hemoglobin, reticulocyte count (Part 2 only), lactate, PT/INR and aPTT levels will also be assessed at screening.

To further permit assessment of modulation of oxygen affinity and possibly limit excessive pharmacological effect, measures of hemoglobin oxygen affinity (p20 and p50) will be

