10. Baseline 12-lead ECG that demonstrates clinically relevant abnormalities that may affect participant safety or interpretation of study results (eg, baseline QTc interval >450 msec, complete left bundle branch block (LBBB), signs of an acute or indeterminate-age myocardial infarction, ST-T interval changes suggestive of myocardial ischemia, second- or third-degree atrioventricular (AV) block, or serious bradyarrhythmias or tachyarrhythmias). If the baseline uncorrected QT interval is >450 msec, this interval should be rate-corrected using the Fridericia method and the resulting QTcF should be used for decision making and reporting. If QTc exceeds 450 msec, or QRS exceeds 120 msec, the ECG should be repeated 2 more times and the average of the 3 QTc or QRS values should be used to determine the participant's eligibility. Computer-interpreted ECGs should be overread by a physician experienced in reading ECGs before excluding participants.
11. Participants with ANY of the following abnormalities in clinical laboratory tests at screening, as assessed by the study specific laboratory and confirmed by a single repeat test, if deemed necessary:
 - AST or ALT level $\geq 1.5 \times$ ULN;
 - Total bilirubin level $\geq 1.5 \times$ ULN; participants with a history of Gilbert's syndrome may have direct bilirubin measured and would be eligible for this study provided the direct bilirubin level is \leq ULN;
 - PT/INR $>1.2 \times$ ULN;
 - aPTT $\geq 1.5 \times$ ULN;
 - Hemoglobin <11.0 g/dL;
 - Lactate $>1 \times$ ULN.
12. For Part 2 only, participants with absolute reticulocyte count $>150,000/\mu\text{L}$ at screening, as assessed by the study specific laboratory and confirmed by a single repeat test, if deemed necessary.

Other Exclusions:

13. History of alcohol abuse or binge drinking and/or any other illicit drug use or dependence within 6 months of Screening. Binge drinking is defined as a pattern of 5 (male) and 4 (female) or more alcoholic drinks in about 2 hours. As a general rule, alcohol intake should not exceed 14 units per week (1 unit = 8 ounces (240 mL) beer, 1 ounce (30 mL) of 40% spirit or 3 ounces (90 mL) of wine).

14. Use of tobacco/nicotine containing products for Part 1 or 2, and use of more than 5 cigarettes/day for Part 3.
15. Blood donation (excluding plasma donations) of approximately 1 pint (500 mL) or more within 60 days prior to dosing.

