6.6.1. Dose Escalation and Stopping Rules

Dose escalation stopping rules will be used to determine whether the maximal tolerated dose has been attained. Dose escalation may be stopped if it is determined that the limits of safety and/or tolerability have been reached. This decision will be made after a discussion takes place between the sponsor study team and the investigator. The sponsor study team may not overrule the investigator's decision to stop dose escalation. If dose escalation is stopped because of any of these criteria, additional cohorts may receive the same or lower doses of the study intervention.

The dose escalation will be terminated based on the following criteria:

- If 50% or more of the participants receiving active drug at a given dose level (but not participants receiving placebo) develop similar clinically significant laboratory, ECG, or vital sign abnormalities (as described in [Appendix 8: Criteria for Vital Signs Abnormality](#)), in the same organ class, indicating dose-limiting intolerance.

- If post-treatment p50 values in 2 or more of the participants receiving active drug at a given dose level (but not participants receiving placebo), drops below 20 mmHg, in association with one or more of the following, in any of the respective participants:
 - Treatment emergent increase in EPO above the upper limit of reference range (Part 2 only).
 - Treatment emergent increase from baseline in absolute reticulocyte count, with magnitude of increase $\geq 250,000 / \mu\text{L}$ (Part 2 only).
 - Treatment emergent increase in lactate to above upper limit of normal.
- Severe nonserious AEs, considered as, at least, possibly related to study intervention administration, in 2 participants at a given dose level (but not participants receiving placebo), independent of within or not within the same system organ class, indicating dose-limiting intolerance.

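### The Part 2 schedule contradicts itself on the only pre-treatment EPO sample: the main table marks Day 1, but the Day 1 procedure list limits EPO to Days 7 and 14

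*Protocol*

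**What the plan says.** Protocol Section 1.3 gives Part 2 two linked schedules.

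- **Table B (main schedule).** The column header reads "Treatment Phase (all activities at 0H (predose) unless otherwise specified". The EPO row has its first mark on Day 1, and the Screening and Day -1 cells are blank. Footnote j to Days 1, 7 and 14 reads "Refer to [C List of Procedures for Part 2 Study Day 1, 7 and 14](#) for details".
- **List C (procedures on Days 1, 7 and 14).** The EPO row is labelled "EPO (Day 7 and 14 only" and has one mark, at 0 H. Reticulocytes carry the same restriction. Footnote g adds "Safety laboratory and lactate 0 H: For Day 7 and 14 only".

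Other sections bear on the same sample:

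- Section 4.2 lists the added screening tests: "hemoglobin, reticulocyte count (Part 2 only), lactate, PT/INR and aPTT levels will also be assessed at screening". EPO is not among them. On timing, the section says "hence assessments are planned for Part 2, from Day 7 onwards for EPO and reticulocyte count".
- Section 5.2 sets a screening limit for lactate and another that begins "For Part 2 only, participants with absolute reticulocyte count". It sets none for EPO.
- Section 6.6.1 stops escalation if p50 falls below 20 mmHg in two or more active participants together with at least one of three correlates. One is "Treatment emergent increase in EPO above the upper limit of reference range (Part 2 only"; the others are rises in lactate and in reticulocytes.
- SAP Section 6.2.2 takes the laboratory baseline from Day -1 or from the last available pre-dose measurement, whichever is later.

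**The concern.** One schedule asks for a pre-treatment EPO sample, and the list it defers to for that day excludes it. No other section supplies a baseline: EPO is not a screening test, is not drawn on Day -1, and is not an entry criterion.

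Section 2.3.1 names EPO as a monitor for tissue hypoxia, and the stopping rule asks whether an increase is treatment emergent. With no earlier value, an above-range result on Day 7 or Day 14 can be misread in either direction. A high value that was there before dosing could help to stop escalation, or a real rise could be dismissed as pre-existing. The change-from-baseline summaries would also lack EPO. A predose sample that was not taken cannot be recovered once dosing has begun.

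**Working it through.** **1. Which day does table B mark?** Count cells to the right of the row label. Four anchors fix the early columns.

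- Informed consent is in cell 1 (Screening).
- CRU confinement starts in cell 2 (Day -1).
- The first marks for dosing, PK and p20/p50 are in cell 3 (Day 1).
- The marks that footnote k assigns to Days 4 and 10 are in cells 6 and 12 of the ECG row. Since 6 - 3 = 3 and 12 - 9 = 3, Day 1 is again cell 3.

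The EPO row has its first mark in cell 3 and its second in cell 9. These are Day 1 and Day 7 (9 - 2 = 7). Cells 1 and 2 are empty.

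**2. Is the conflict specific to EPO?** The two schedules side by side:

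| Row | Screening and Day -1 (B) | Day 1 (B) | Day 1 (List C) |
|---|---|---|---|
| EPO | none | yes | none |
| Reticulocytes | both | no | none |
| Ferritin and CRP | both | no | none |
| Urinalysis | both | no | none |
| Safety laboratory | both | yes | 8 h only |
| Lactate | both | yes | 8 h only |
| p20 and p50 | none | yes | 0 H and 8 h |

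Reticulocytes, ferritin/CRP and urinalysis have no Day 1 mark in table B, so List C does not contradict it for them. Safety laboratory and lactate lose the 0 H sample on Day 1 but keep one at 8 h. All five have Screening and Day -1 samples.

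Table B has 9 unredacted rows with an X on Day 1: ECG, supine blood pressure and pulse, orthostatic blood pressure with respiratory rate and temperature, dosing, safety laboratory, lactate, EPO, PK, and p20/p50. Eight of them have a Day 1 time in List C. EPO is the only one that does not.

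**3. Pre-treatment EPO samples per participant.** One under table B (Day 1 predose), none under List C.

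**4. Does Section 4.2 settle it?** Its Day 7 wording can be read as agreeing with List C. The support is weak, because it says the same of reticulocytes, which table B samples at Screening and Day -1.

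**5. Participants concerned.** Section 4.1 plans about 6 active of 8 per cohort. Three cohorts give 3 x 6 = 18 of 24; five give 5 x 6 = 30 of 40.

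**6. Illustration of the attribution problem.** The documents give no rate of above-range EPO in untreated healthy adults. Assume p = 2.5% (range 1% to 5%), independent between participants. Given n participants with p50 below 20 mmHg, the chance that at least one already had an above-range EPO is 1 - (1 - p)^n.

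| n | p = 1% | p = 2.5% | p = 5% |
|---|---|---|---|
| 2 (minimum for the rule) | 2.0% | 4.9% | 9.8% |
| 6 (all active in a cohort) | 5.9% | 14.1% | 26.5% |

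For example, 1 - 0.975^2 = 0.049 and 1 - 0.975^6 = 0.141.

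**The case against.** **The Day 1 reading rests on one cell in a table that reads imperfectly as text.** The dosing row shows 17 marks for a 14-day regimen. The orthostatic row has its Day 7 mark one cell too far right, and later marks in other rows are also displaced. If the first EPO mark had slipped one cell to the right, it would belong to Day -1. EPO would then match List C and have a baseline. This cannot be excluded from the text alone. It is the less natural reading, because the second EPO mark sits where Day 7 belongs, so the slip would have to be undone within the same row. The orthostatic row, which does slip, still starts in the Day 1 cell. The mark should be confirmed on the laid-out page.

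**Table B schedules a pre-treatment sample on either reading.** This stands. The baseline is lost only if a site follows List C, but footnote j directs the site there for Day 1.

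**The stopping rule does not depend on EPO alone.** This also stands. The EPO limit is absolute, lactate and reticulocytes have baselines, and Section 6.6.1 lets the team halt escalation for other findings. A high EPO of unknown origin could be counted as emergent, but no section says so, and the SAP baseline would still be missing.

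**The percentages are not trial risks.** Correct. They are conditional on participants already having p50 below 20 mmHg, and the documents give no probability for that. The contradiction does not depend on them.

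**Conclusion.** The contradiction holds. Table B schedules one pre-treatment EPO sample and List C schedules none. EPO is the only one of the 9 Day 1 rows affected, and the only one of the six laboratory rows compared that could end up with no pre-treatment value.

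The effect is limited to one of three alternative correlates, in about 18 active participants (30 with the optional cohorts), and only where List C is followed. It weakens attribution of an EPO rise and removes the EPO baseline, but leaves the rest of the p50 rule intact. It should be corrected because the sample cannot be obtained later.

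Confidence is medium. The List C wording is explicit, while the Day 1 mark in table B depends on the column alignment described above. The illustrative probabilities also assume the above-range rate and independence.

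**What to change.** Make table B, List C and Section 4.2 agree on EPO sampling, so that every Part 2 participant has a pre-treatment EPO value for the treatment-emergent criterion in Section 6.6.1 and for the baseline in SAP Section 6.2.2. No change to any threshold or stopping rule is proposed.

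The cost is a few words in the schedule tables and in Section 4.2, plus at most one small sample per Part 2 participant. List C already draws blood at 0 H on Day 1 for PK and p20/p50, so a Day 1 sample could share that time point. If it is not already counted in the blood volume of about 529 mL in Section 8, check it against the 550 mL ceiling there (550 - 529 = 21 mL to spare).
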